12.5.2 Completing the Implant Visit

1. Program the device according to physician discretion
2. Print the ‘Quick Notes’ Report

12.5.3 Implant Source Data Requirements

Source data requirements at implant are described in Table 12-4.

Table 12-4: Implant Source Documentation Requirements

Source Documentation Requirement	Disposition
Device model/serial number	Retain at center
Lead model/serial numbers for all implanted leads	
Device Evaluation (pace thresholds, sense amplitudes, impedances, RV shock impedance)	
PRM ECG strips from manual threshold tests documenting LOC for all implanted leads	
Printout of ‘Quick Notes’ Report	
Adverse Events	

12.6 Pre-Discharge

For Phase I de novo subjects, the Pre-discharge Visit will occur either on the same day as the ImageReady System implant procedure, a minimum of 3 hours after pocket closure, or up to 72 hours after the implant procedure.

12.6.1 Device Evaluation

All implanted leads will be evaluated through the implanted PG using the test parameters listed in Table 12-3:

- Manual pacing threshold tests, as defined in sections 12.5.1.1, 12.5.1.2 and 12.5.1.3.
- Sensing amplitude

- Impedance
- Shock impedance (RV lead only)

Record the measurements in the EDC system.

12.6.2 Completing the Pre-Discharge Visit

1. Program the device according to physician discretion
2. Print the 'Quick Notes' Report
3. Schedule the MRI follow-up visit

12.6.3 Pre-Discharge Source Data Requirements

Source data requirements at Pre-discharge Visit are described in Table 12-5:

Table 12-5: Pre-Discharge Source Documentation Requirements

Source Documentation Requirement	Disposition
Device Evaluation (pace threshold, sense amplitude, impedance, RV shock impedance)	Retain at center
PRM ECG strips from manual threshold tests documenting LOC for all implanted leads	
Printout of 'Quick Notes' Report	
Adverse Events	

12.7 MRI Visit (Phase I only)

The MRI follow-up visit consists of data collection and MR scan.

For Phase I de novo subjects, the visit will occur 6 to 9 weeks (42-63 days) after implant or surgical revision of the ImageReady System implant*.

For Phase I existing implant subjects, the visit will occur **within 6 weeks** (42 days) from enrollment AND at least 6 weeks after implant or surgical intervention* of the ImageReady System. For example:

- If the subject was enrolled with an ImageReady System that was implanted >6 weeks before enrollment, the MRI visit must occur within 6 weeks (42 days).
- If the subject was enrolled with the an ImageReady System that was implanted 2 weeks (14 days) before enrollment, the MRI visit must occur between 4 – 6 weeks (28 to 42 days) after enrollment.

***Note:** If a subject has had a surgical revision to their ImageReady System (i.e., a lead revision/ reposition), and the MRI Visit is unable to be scheduled within the time window, the MRI Visit and the MRI + 1 Month Visit are not required. Enter the reason for MRI Visit and MRI + 1 Month visit not being done into EDC.

Note: For subjects enrolled under prior protocol versions and who have not been through their MRI visit, the MRI visit will occur within 6 weeks (42 days) from re-consenting and after reconfirmation that they do not meet the exclusion criterion #5

12.7.1 Device Evaluation Prior to Commencement of MR Scan

1. All implanted leads will be evaluated through the implanted PG for **THREE separate consecutive sets of measurements** using the test parameters listed in Table 12-3:
 - Manual pacing threshold tests, as defined in sections 12.5.1.1, 12.5.1.2 and 12.5.1.3.
 - Sensing amplitude
 - Impedance
 - Shock impedance (RV lead only)
2. Test for phrenic nerve stimulation (PNS) and measure the PNS threshold if detected in the programmed LV lead configuration
3. Perform an assessment of Beeper function as defined in section 12.7.1.1.
4. Print the 'Quick Notes' Report

Record the measurements in the EDC system.

12.7.1.1 Assessment of Beeper function

To test if the Beeper is audible,

1. Program Magnet Response to Inhibit Therapy
2. Place the magnet over the PG for a minimum of 5 seconds but not for more than 20 seconds in a quiet environment.
 - If the Tachy mode is programmed to 'Monitor + Therapy': A short beep may be heard once every second, as long as the magnet is placed over the PG.
 - If the Tachy mode is programmed to 'Monitor only' or 'OFF': A continuous beep may be heard as long as the magnet is placed over the PG.

Note: The Magnet Sensor will detect Guidant/Boston Scientific CRM magnets (donut, horseshoe or wrist) within 3 cm. The Magnet Sensor will detect a 60 G < field ≤300 G, when applied perpendicularly to the surface of the PG, either face.

3. The subject and the HCP will be asked to indicate whether the Beeper is audible to them.
4. If not audible, by either the subject or the HCP, a second attempt at assessing Beeper function will be performed. The Beeper should be assessed in the alternate Tachy mode (as listed in step 2) if tolerated by the subject.
5. Record if the Beeper was audible by the subject and the HCP in the EDC..

12.7.2 Subject Evaluation Prior to Commencement of MR Scan

12.7.2.1 Confirmation of MRI Conditions of Use

Subjects must meet the MRI Conditions of Use, comprised of Cardiology and Radiology Conditions of Use, as listed in the *BSC MRI Technical Guide* and Section 6 of this protocol.

Documentation of both the Cardiology and Radiology MRI Conditions of Use assessment must be included.

Note: Subjects must satisfy the MRI Conditions of Use prior to receiving the study-required MR scan; otherwise a protocol deviation shall be assessed.

12.7.2.2 Subject History of Unexplained Syncope

Prior to the MR Scan, subjects should be questioned or a current medical history review should occur to determine if there is any history of unexplained syncope (loss of consciousness). If confirmed, the subject should not proceed with the study-required MR scan and be withdrawn from the study.

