10.3 Exclusion Criteria

Subjects who meet any one of the following criteria (Table 10-2) will be excluded from this clinical study.

Table 10-2: Exclusion Criteria

Exclusion Criteria	1. Subject implanted with an ICD or CRT-D pulse generator with battery at Explant status
	2. Subject has other active or abandoned implanted cardiac rhythm devices, components or accessories present such as pulse generators, leads, lead adaptors or extenders
	3. Presence of metallic objects that represent a contraindication to MR imaging at the discretion of the Radiologist and impacting the ability to conduct the study protocol
	4. Subject needs or will need a medically necessary MR scan, before completing the 1-month post-MR follow-up visit (Phase I only)
	5. Subject with: 
 • A history of syncope related to brady-arrhythmia • A history of syncope of unknown etiology • Sinus pauses (Pause > 2 s) • Permanent or intermittent complete AV block • Documentation of progressive AV nodal block over time • Trifascicular block (alternating bundle branch block or PR > 200 ms with LBBB or other bifascicular block) 
Note: It is required to run a 12 lead ECG and a 10s rhythm strip to document this exclusion criterion. During ECG acquisition, subjects must be in either their own intrinsic rhythm or, in subjects with an existing device implant, the device must be programmed to VVI 40 ppm.

	6. Subject is not clinically capable of tolerating the absence of pacing or Resynchronization therapy support in a supine position for the duration that the pulse generator is in MRI Protection Mode, per Physician discretion
	7. Subject is not clinically capable of tolerating the absence of Tachycardia therapy support for the duration that the pulse generator is in MRI Protection Mode, per Physician discretion
	8. Subjects with a planned RA, RV or LV lead revision or extraction within 30 days of enrollment (Phase I only)
	9. Subjects with an implanted lead that is planned to be extracted during the study implant procedure
	10. Subjects currently requiring dialysis
	11. Subject has a mechanical heart valve
	12. Subject has a known or suspected sensitivity to dexamethasone acetate (DXA)
	13. Subject is currently on the active heart transplant list

	14. Subject has documented life expectancy of less than 12 months

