11.1 Screening and Point of Enrollment

11.1.1 Subjects enrolled under previous protocol versions

All subjects enrolled under previous protocol versions will need to be re-consented. The exclusion criterion #5 will need to be evaluated for these patients:

- Subjects not having performed the MRI visit:
 - If these subjects meet the updated exclusion criterion #5, they should be withdrawn from the study and classified as consent ineligible subjects. These withdrawn subjects will not count against the enrollment ceiling.
 - If these subjects do not meet the updated exclusion criterion #5:
 - They will continue as part of Phase I and will undergo the non-diagnostic study required MR scan
 - If they refuse to undergo the non-diagnostic study required MR scan (Phase I), they will automatically be rolled onto Phase II unless they

chose to withdraw from the study. These withdrawn subjects will not count against the enrollment ceiling.

- Subjects having performed the MRI visit:
 - If these subjects do not meet the updated exclusion criterion #5, they will continue in the study and attend visits as required per protocol. These subjects are counting toward the enrollment ceiling.
 - If these subjects meet the updated exclusion criterion #5, this should be documented in the subject’s file. These subjects can remain enrolled in the study. In case of withdrawal, if possible, such subjects should not be withdrawn prior to the MRI + 1 month to ensure safety follow-up within 30 days post MRI. These subjects are counting toward the enrollment ceiling.

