12.3 Informed Consent

All subjects who complete the informed consent process, sign and date the informed consent form will be evaluated for the following criteria:

- Radiologist approval to undergo MRI scan if metal objects in body (exclusion criterion #3)
- 12 lead ECG and 10s rhythm strip (either from the ECG machine or the BSC PRM) (exclusion criterion #5)

Source documentation for both of these exclusion criteria need to be retained in the patient medical file.

Subjects who meet these exclusion criteria will be considered Consent ineligible and will not count toward the enrollment ceiling.

Subjects who do not meet these exclusion criteria will be considered enrolled in the ENABLE MRI study and will count toward the enrollment ceiling.

In addition, subjects who meet none of the exclusion criteria for the VF Induction Sub-study and undergo the VF Induction Sub-Study informed consent process, sign, and date the ENABLE MRI VF Induction Sub-study informed consent form are considered enrolled in the Sub-study.

For Phase I de novo implants: Enrollment may occur up to 30 days prior to the implant procedure.

A summary of the data collected at enrollment is described in Table 12-1. The following assessments will be performed at Enrollment.

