12.7.6 MRI Visit Source Data Requirements

Source data requirements at the MRI Visit are described in Table 12-6:

Table 12-6: MRI Visit Source Documentation Requirements

Source Documentation Requirement	Disposition
Pre-MR scan: 
 • Assessment of patient history of unexplained syncope • Device Evaluation (pace threshold, sense amplitude, impedance, RV shock impedance, LV Phrenic Stimulation threshold) • PRM ECG strips from manual threshold tests documenting LOC for all implanted leads • Assessment of Beeper function • Printout of ‘Quick Notes’ Report • Cardiology and Radiology MRI Conditions of Use are satisfied • 12 leads ECG & 10s rhythm strip (either from the ECG machine or the BSC PRM) 	Retain at center
While PG is programmed to MRI Protection Mode: 
 • MRI Protection Settings Report • Heart rate, blood pressure, Oxygen saturation levels, and Voice Contact in 5 ± 2 minute intervals 	Retain at center

Source Documentation Requirement	Disposition

 • Rhythm strip every 5 ± 2 minutes (recommended) • Rhythm strips for abnormal rhythms, as applicable (recommended) • Medications used for sedation in the MR scanner, if applicable • MR Scanner manufacturer and model • Time of MR scan initiation • Time duration for each sequence within the RF intensive and Gradient intensive scans • Total duration of RF intensive scan sequences • Total duration of Gradient intensive scan sequences • Time of MR scan completion 	
When PG is programmed out of MRI Protection Mode: 
 • Time of exiting MRI Protection Mode 	Retain at center
Post-MR scan: 
 • Device Evaluation (pace threshold, sense amplitude, impedance, RV shock impedance, LV Phrenic Stimulation threshold) • PRM ECG strips from manual threshold tests documenting LOC for all implanted leads • Assessment of Beeper function • Document if polymorphic or monomorphic VT/VF episodes requiring therapy, are present • Documentation of spontaneous VT/VF episode(s) by PRM strips, as applicable: 
 ○ ‘Selected Episodes Report’ (counters and EGMs required) ○ ‘Arrhythmia Logbook’ • Printout of ‘Quick Notes’ Report 	Retain at center
Adverse Events	Retain at center

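### The MRI Visit history check stops the Phase I scan only for unexplained syncope, although exclusion 5 also bars syncope related to brady-arrhythmia

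*Combined protocol and SAP*

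**What the plan says.** Exclusion criterion 5 (section 10.3, Table 10-2) has six items. Two are syncope histories: "A history of syncope related to brady-arrhythmia", and syncope whose cause is not known. The other four are sinus pauses longer than 2 s, complete AV block, progressive AV nodal block and trifascicular block. Exclusion 6 adds a physician's judgement: "Subject is not clinically capable of tolerating the absence of pacing or Resynchronization therapy support in a supine position" while the device is in MRI Protection Mode.

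Criterion 5 is applied once consent is signed. Section 12.3 states: "Subjects who meet these exclusion criteria will be considered Consent ineligible and will not count toward the enrollment ceiling". Subjects from earlier protocol versions who have not yet been scanned are checked against it again. Section 11.1.1 states: "If these subjects meet the updated exclusion criterion #5, they should be withdrawn from the study and classified as consent ineligible subjects". Section 12.7 lets their MRI Visit take place only "after reconfirmation that they do not meet the exclusion criterion #5".

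At the MRI Visit, section 12.7.2.2 calls for questioning or a record review to "determine if there is any history of unexplained syncope (loss of consciousness". The consequence follows: "If confirmed, the subject should not proceed with the study-required MR scan and be withdrawn from the study". The matching source item in Table 12-6 is "Assessment of patient history of unexplained syncope". Sections 12.7.2.3 and 12.7.3.2 then require two rhythm observations, one at VVI 40 before MRI Protection Mode is programmed and one after, with their own lists of disqualifying findings.

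**The concern.** The entry rule treats both syncope histories as disqualifying, but the MRI Visit rule carries forward only one. Followed to the letter, section 12.7.2.2 withdraws a subject whose faint is unexplained. It does not stop a subject whose faint has been worked up and attributed to bradycardia. That is the wrong way round for this exposure: section 5.1.1 suspends bradycardia pacing in MRI Protection Mode, and section 12.7.3 describes the Phase I scan as non-diagnostic research. Section 20.4 lists bradycardia, syncope and death among the possible events even when the Conditions of Use are met. Subject safety is at stake here; the statistical result is not.

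**Working it through.** No sample-size, power or alpha figure bears on this point. The check is a mapping of exclusion 5 onto the MRI Visit steps.

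| Exclusion 5 item | Asked as history at the MRI Visit | Stops the scan if seen during rhythm observation |
|---|---|---|
| Syncope related to brady-arrhythmia | No | Only if a listed rhythm shows at that time |
| Syncope of unknown cause | Yes: 12.7.2.2, Table 12-6 | Not applicable |
| Sinus pause > 2 s | No | 12.7.3.2 by name; 12.7.2.3 through a paced beat |
| Complete AV block | No | 12.7.2.3 and 12.7.3.2 |
| Progressive AV nodal block | No | 12.7.2.3 and 12.7.3.2 |
| Trifascicular block | No | 12.7.2.3 and 12.7.3.2 |

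**History.** The bracketed gloss in 12.7.2.2 only explains the word syncope. The section heading, its text and Table 12-6 all keep the qualifier *unexplained*, so a faint with a known brady cause lies outside the rule.

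**Observation.** At VVI 40 the device paces after 60 s / 40 = 1.5 s without a ventricular event, and one paced beat disqualifies. The check is therefore sensitive while it runs. Its guaranteed length is 2 × 5 = 10 minutes, and both sections limit the stop to what appears in that time. A pause or an intermittent block documented since enrollment but absent in those minutes is not a named stop either.

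**Who is rechecked.** Sections 11.1.1 and 12.7 require exclusion 5 to be reconfirmed for unscanned subjects from earlier versions. No visible text asks the same for subjects enrolled under version AE or later. Section 11.1.2, which covers them, is redacted.

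**What else protects the subject.** Condition of Use 5 (section 6.1) requires a judgement that the patient can tolerate having no bradycardia support, and section 12.7.2.1 requires this to be met and documented before the scan. Exclusion 6 and withdrawal at the physician's discretion (section 11.2) point the same way. Sections 12.7.3.1 and 12.7.3.3 add continuous investigator monitoring, an external defibrillator with trained staff, and a programmer kept on nearby. Active scanning is capped at 35 minutes (section 28.3).

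**The case against.** The strongest reply is that a mandatory, documented gate already exists. An investigator who knows of brady-arrhythmic syncope would find it hard to certify Condition of Use 5, and 12.7.2.2 is itself worded as *should*. This largely stands as protection, but the gate rests on judgement. The Phase I note to Condition 5 defines pace-dependence as having no underlying rhythm at VVI 40, so a subject with intermittent bradycardia who is in intrinsic rhythm that day is not pace-dependent under it. The sponsor chose not to leave unexplained syncope to judgement alone.

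Second, a history that predates enrollment already meets exclusion 5, and section 11.3.2 can be read as making such a subject consent ineligible whenever it comes to light. That reading is fair. For that group the MRI Visit lacks a prompt, not a rule.

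Third, the implanted device normally paces outside MRI Protection Mode. New brady-arrhythmic syncope after implant would then suggest a pacing failure, which Condition of Use 9 on system integrity addresses. This stands, except that programming is at the physician's discretion (section 12.5.2).

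Fourth, the redacted section 11.1.2, or the MRI Technical Guide that section 12.7.2.1 also invokes, may contain the missing rule. That cannot be excluded. It would not change the wording of 12.7.2.2, but a cross-reference might then be all that is needed.

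**Conclusion.** The inconsistency is real but small. The visible MRI Visit history check is narrower than exclusion 5, and the rhythm stops do not turn the remaining items into a history check. This is a gap in an explicit rule, not an absence of protection. The documents give no count of affected subjects. Few are likely, and no endpoint definition, hypothesis or test is touched. It is a low-severity, cheap improvement.

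Two stronger readings are tempting, and the documents do not support them.

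- A reader might infer that brady-arrhythmic syncope is the single exclusion 5 item left open and that the other five are fully covered. They are not: pauses and intermittent blocks that occur between visits have much the same gap.
- A reader might add up the visit windows for de novo subjects (0 + 42 = 42 to 30 + 63 = 93 days from enrollment to scan, and up to 42 days for existing implants) and call the result an unprotected period. It is not one. Existing-implant subjects have a working system throughout, and de novo subjects have one after implant. Only the 0 to 30 days before a de novo implant lack the new device's pacing. Subjects from earlier versions may also have a gap, because section 12.7 does not place their reconfirmation at the visit itself.

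The conclusion assumes that the redacted section 11.1.2 and the Technical Guide contain no equivalent rule.

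**What to change.** The minimum change is to reword section 12.7.2.2 and the Table 12-6 item to *any history of syncope that is unexplained or related to brady-arrhythmia*, keeping the same consequence.

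The preferable change is to require, for all Phase I subjects at the MRI Visit, confirmation by history that no exclusion 5 item has been met since enrollment. This also covers a documented pause or intermittent block that does not recur during the observations, and it brings subjects enrolled under version AE or later into line with the reconfirmation already asked of earlier ones. If section 11.1.2 already says this, a cross-reference from 12.7.2.2 is enough.

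The cost is one question on the source form and no extra procedure, since the history is already being taken. Rarely, one more subject goes unscanned. Section 13.1.1.3 already treats unscanned subjects as missing data in the safety tipping-point analysis.

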12.7.2.3 Heart Rhythm Monitoring prior to MRI protection mode programming

It is **required** that the heart rhythm be monitored by the site Principal Investigator or a sub-investigator for all subjects prior to initiation of the MRI Protection Mode and the MR Scan.

- Monitoring is to be performed in VVI 40 programming
- Monitor the heart rhythm using the programmer EGRAMs for at least 5 minutes. Heart rate and any abnormal rhythms, including incidence of ectopy shall be documented.
 - In particular, look for signs of progressive AV nodal block over time, permanent or intermittent complete AV block, or trifascicular block (alternating bundle branch block or PR > 200 ms with LBBB or other bifascicular block) or a paced event (one single paced beat) during this time period. **Any** occurrence of these events will disqualify subjects from undergoing the MRI.
 - Such subjects should be withdrawn from the study.
 - Required ECG documentation
 - 12 lead ECG and a 10s rhythm strip to be printed at any time during the 5 minutes of the monitoring (either from the ECG machine or the BSC PRM)
 - Any abnormal rhythms / ectopy shall be documented with a printed ECG or rhythm strip if possible.

12.7.3 MR Scans

The MR scan must be performed within the guidelines of this protocol and the *BSC MRI Technical Guide*. When differences exist, the ENABLE MRI Study protocol extends the *BSC MRI Technical Guide*.

MRIs must be performed in 1.5 Tesla, closed bore scanners with body coil excitation. Subjects will complete MR scans per the MR scan sequences protocol in Section 28 of this protocol.

Note: Incidental findings are defined as a “finding concerning an individual research participant that has potential health or reproductive importance and is discovered in the course of conducting research but is beyond the aims of the study¹⁰”. The MR scans required by the ENABLE MRI Study are not intended for diagnostic purposes. Therefore, they are not intended or required to be read by trained radiologists. If the site’s MR technician performing the scan determines any incidental findings, or if a site’s procedures dictate that MR scans must be read, any incidental findings must be reported to the site’s primary investigator by the person who reads the scan.

Additionally, it is important to note that the Image Artifact core lab (see Section 14.3) will not be required or requested to report incidental findings to BSC or the investigator, and BSC will not be reviewing any images received for diagnostic or incidental finding purposes.

Site investigators must make it clear through the patient informed consent process that the MR scans required by the ENABLE MRI Study are for research only. They are not intended for diagnostic purposes, and will not necessarily be viewed by trained professionals.

